## **Background**

The Our Care Wishes (OCW) platform has undergone extensive mixed-methods testing and is already in use by health systems and in RCTs. OCW was rigorously developed and refined to optimize ACP completion rates. It has been tested among more than 3,000 patients. More than 70% of patients who have engaged with the platform have completed an ACP, and the sites Net Promotor Score, a standard measure that assesses the users likelihood to recommend a product or service, is 80%. The platform also has a back-end interface that enables care plans to be automatically uploaded into EHRs. It is being studied in an ongoing RCT of ACP for bone-marrow transplantation patients. These findings support the feasibility of having PWD and their caregivers complete OCW, as well as the need for further refinement of the content to meet the needs of PWD.

## **Study Design**

### **Design**

Our application is grounded in the Ecological Model of Patient Centered Communication. There is a growing body of research demonstrating that aligned and documented ACP communication is associated with better outcomes for PWD. Aim 1: Tailor the OCW platform. Several adaptations are needed to ensure that OCW: 1) specifically addresses end-of-life issues for PWD and their SDMs; 2) aligns with the legal requirements and ethical principles involved in surrogate decision-making; 3) addresses the needs of diverse users; and 4) integrates seamlessly with the PointClickCare EHR used by all Genesis facilities and most NHs nationwide. To meet these goals, we will convene a stakeholder group of clinicians with expertise in NH and dementia care, PWD and their family caregivers, an ethicist, and an eldercare attorney. This group will advise us on content and the interface. The group will meet 7-8 times over 4 months using Blue Jeans videoconferencing software. All meetings will be audiotaped to capture the full group discussion and decisions. The goal of the web-based meetings is to reach consensus on the content and interface of the adapted website. We expect that the elements suggested for revision will include content regarding: 1) principles of shared decision-making; 2) the role of caregivers as SDMs; 3) the natural progression of dementia; 4) common end-of-life decisions; and 5) the benefits and burdens of interventions for PWD. Aim 2: Examine the user interface and acceptability of the OCW-Dementia platform. To evaluate the acceptability and usefulness of the platform, we will recruit up to 10 Genesis staff members (based on suggestion from Genesis management), and they will assent to comment on the platform and accompanying Qualtrics surveys. Study team members will interview Genesis staff on their reactions to the platform and surveys and take notes on the reactions. These interviews will take place virtually via BlueJeans and will not be recorded. Staff will not submit or discuss any identifiable information and will be instructed to not discuss any identifiable information of patients/residents of Genesis. The website and survey links will be emailed to Genesis staff and they will review the website and surveys prior to the interviews. At the beginning of the interview, study team members will confirm Genesis staff assent to participation and remind them

that their participation is completely voluntary and can be ended at any time. Each session will last up to half an hour. To evaluate the acceptability and usefulness of the platform, we will also recruit up to 15 Healthy Patterns Sleep Study participants (IRB protocol # 825000) for virtual beta testing of the website. Participants will be selected if they have previously agreed to being contacted for research and if they have a computer or smartphone on which to view the website and surveys. Participants will be recruited as dyads (caregiver and person with dementia). Dyads will consent to the study staff contacting them via phone or BlueJeans and guiding them through the website and accompanying Qualtrics surveys. Qualtrics surveys will be administered before and after the viewing of the website; surveys will ask dyads for their feedback on the website and their confidence making decisions about future care. Virtual beta testing platforms will depend on the participants' ability and resources, and may include telephone, Skype, FaceTime, or BlueJeans and any internet browsers. Study staff will take notes on the reactions of dyads in order to improve the website and user experience after beta testing. When filling out the surveys, no identifiable information will be collected. The calls and/or video chats will not be recorded. Each Healthy Patterns participant within each dyad will receive \$15 via Greenphire gift cards at the end of study participation. Gift cards will be mailed to dyads. Each session will last up to an hour. Some identifiable information (name, DOB, email address, phone number, address) will be entered in the website but will not be used or recorded in the study. The website is hosted by Pantheon, which is a Penn approved hosting platform. The site is encrypted with SSL (Secure Sockets Layer) to protect participant information. Aim 3: Randomized Pilot. Setting/sample. We will conduct the pilot study in up to four Genesis facilities with diverse locations (urban, suburban, rural). We will also include at least one facility that serves mostly minority populations to test the effectiveness of the OCW-Dementia module among racially and ethnically diverse PWD. We will recruit up to 50 patients/residents and their SDMs. Eligible PWD will be receiving short- or long-term care at a participating NH, have documented moderate to severe cognitive impairment and have an identified SDM. We will exclude residents clearly exhibiting terminal decline, thereby reducing the likelihood of attrition. Study team members will work with Genesis staff to recruit dyads (Genesis residents and their family members or supportive decision-makers (SDMs) who are interested in participating in the study. Study team will read an assent script to interested SDMs, gain verbal assent and then send SDMs the study summary and copy of the assent script. After verbal assent is acquired, dyads will be assigned to the intervention group or usual care arm. At each site, up to 10 dyads will be recruited. Half of the dyads recruited at each site will receive their usual care and complete the demographics survey, COVID-19 survey and pre and post confidence in decision making surveys. The second half of dyads recruited at each site will receive the intervention as well as complete the demographics survey, COVID-19 survey and pre and post confidence in decision making surveys.

#### **Study duration**

Participation will last up 1 hour per session. There will be two sessions total. Study recruitment will begin in August of 2020 and end by November of 2020. All study activities will end December 2020.

## **Characteristics of the Study Population**

#### **Target population**

Persons with dementia and their surrogate decision makers.

#### **Subjects enrolled by Penn Researchers**

50

#### **Subjects enrolled by Collaborating Researchers**

0

## **Vulnerable Populations**

**Children Form**

**Pregnant women (if the study procedures may affect the condition of the pregnant woman or fetus) Form**

**Fetuses and/or Neonates Form**

**Prisoners Form**

**Other**

**None of the above populations are included in the research study**

## **The following documents are currently attached to this item:**

*There are no documents attached for this item.*

## **Subject recruitment**

For Aim 2, Genesis staff members recruited will be those recommended by Genesis management. Additional participants will be recruited from the Healthy Patterns Sleep Study (IRB Protocol 825000) who have agreed to be contacted for future research. These participants (dyads) are persons with dementia with caregivers in the greater Philadelphia area who will have access to a smartphone or computer. We will conduct the pilot study in up to four Genesis facilities with diverse locations (urban, suburban, rural). We will also include at least one facility that serves mostly minority populations to test the effectiveness of the OCW-Dementia module among racially and ethnically diverse PWD. We will recruit up to 50 patients/residents and their SDMs. Eligible PWD will be receiving short-or long-term care at a participating NH, have documented moderate to severe cognitive impairment and have an identified SDM. We will exclude residents clearly exhibiting terminal decline, thereby reducing the likelihood of attrition. Strategies to address potential study limitations. If we are unable to rapidly recruit sufficient numbers of PWD and SDMs at up to four facilities for Aim 3, we will work with Genesis leaders to expand recruitment to additional facilities. There are 25 Genesis facilities within a 25-mile radius of the Penns campus. For Aim 3, Study team members will work with Genesis staff to recruit dyads, ie. Genesis residents and their supportive decision-makers (SDMs) who are interested in participating in the study. Study team will read an assent script to interested SDMs, gain verbal assent and then send SDMs the study summary and copy of the assent script. After verbal assent is acquired, dyads will be randomized to the intervention group or usual care arm. At each site, up to 10 dyads will be recruited. Half of the dyads recruited at each site will receive their usual care and complete the demographics survey, COVID-19 survey and pre and post confidence in decision making surveys. The second half of dyads recruited at each site will receive the intervention as well as complete the demographics survey, COVID-19 survey and pre and post confidence in decision making surveys.

Will the recruitment plan propose to use any Penn media services (communications, marketing, etc.) for outreach via social media avenues (examples include: Facebook, Twitter, blogging, texting, etc.) or does the study team plan to directly use social media to recruit for the research?

No

## **The following documents are currently attached to this item:**

*There are no documents attached for this item.*

## **Subject compensation\***

Will subjects be financially compensated for their participation?

Yes

## **The following documents are currently attached to this item:**

*There are no documents attached for this item.*

**If there is subject compensation, provide the schedule for compensation per study visit or session and total amount for entire participation, either as text or separate document**

Participants recruited from the Healthy Patterns Sleep Study (IRB Protocol 825000) for virtual beta testing will be compensated \$15 each via Greenphire gift cards at the end of study participation. Participants who are residents of Genesis Healthcare and recruited by Genesis Healthcare staff will not receive financial incentive or compensation at the request of the Clinical Project Outcomes Coordinator at Genesis Healthcare.

## Study Procedures

### **Suicidal Ideation and Behavior**

Does this research qualify as a clinical investigation that will utilize a test article (ie- drug or biological) which may carry a potential for central nervous system (CNS) effect(s)?

No

### **Procedures**

Aim 2: For participants recruited in the beta testing trial, study personnel will convene PWDs and their caregivers via video chart to administer the pre-survey and facilitate completion of OCW-Dementia. One week later, study personnel will call PWDs and caregivers to administer the post survey. Participants will be paid after completion of post survey. Aim 3: In the usual care arm, Genesis staff will follow their facilities standard admission policies, which include asking about the presence of advance directives, and offering assistance in completing an AD in accordance with state laws. Staff or study personnel will administer the pre-survey at the time of usual care and then administer the post survey and COVID-19 survey one week later to participants randomized to the usual care arm. In the intervention arm, Genesis staff will convene SDMs and PWDs via phone, video chat or in person, provide tablet computers to PWD and facilitate conversation about the website so that SDMs and PWDs can complete OCW-Dementia. An infection control policy will be implemented for tablet computer usage. Genesis staff or study personnel will administer the pre-survey prior to website completion and administer the post survey and COVID-19 survey one week after website completion

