## Current Status of Study

### Study Status

Closed to subject enrollment (remains active)

*If study is currently in progress, please enter the following*

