### **Analysis Plan**

We will use Z-tests to test our hypothesis that a significantly higher percentage of participants in the intervention group will complete an ACP compared with those in the usual care group. We adjust for participant characteristics due to the small sample size, but only the most important characteristics using likelihood ratio testing to avoid an overfit model. To generate new hypotheses, we will examine differences between groups with regard to demographic and clinical variables using parametric t-tests or nonparametric Wilcoxon tests (for continuous variables) and Fishers Exact tests for binary variables. To explore differences in Decisional Conflict scale scores, we will conduct a two-group independent T-test. Based on estimates derived from the Genesis EHR, we expect that 30% of PWD/SDM in the usual care arm will have a completed ACP within several weeks following admission to participating NHs. In the intervention arm, we estimate that 70% of SDMs/PWD will complete an ACP, as has been found among other OCW users (see Preliminary Studies). Enrolling 25 participants in each arm would yield 91.5% power to detect this difference of 70% vs. 30% ACP completion rate between the intervention and control groups. This calculation is based on a 1-sided Z-test with pooled variance and a significance level of 0.05.

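### Does timing the Aim 3 intervention post-survey to website completion leave non-finishers out of the survey comparison?

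*Combined protocol and SAP*

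**What the plan says.** Procedures sets the Aim 3 survey times separately for each arm. In usual care, staff or study personnel "administer the pre-survey at the time of usual care and then administer the post survey and COVID-19 survey one week later". In the intervention arm, Genesis staff bring the dyad together and "facilitate conversation about the website so that SDMs and PWDs can complete OCW-Dementia"; staff or study personnel give the pre-survey beforehand and "administer the post survey and COVID-19 survey one week after website completion". The protocol does not define website completion and gives no separate rule for a dyad that starts and does not finish.

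Three other places bear on the meaning:

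- Study duration allows up to one hour per session and says "There will be two sessions total".
- Subject recruitment, and the Design section in the same words, say that the intervention half of the dyads at each site "will receive the intervention as well as complete the demographics survey, COVID-19 survey and pre and post confidence in decision making surveys", with no condition on finishing.
- The Aim 2 text in Procedures has staff give the pre-survey and help the dyad complete the website on a video call, with the post-survey by telephone a week later.

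The Analysis Plan says "To explore differences in Decisional Conflict scale scores, we will conduct a two-group independent T-test". It does not say whether the post score or the change score is tested, or that the scale belongs to the pre and post surveys.

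**The concern.** The two arms appear to have different clocks. The usual-care clock starts at the pre-survey and runs for every dyad. The intervention clock starts at an event after randomisation that some dyads may never reach. If completion means a finished OCW-Dementia document, a dyad that stops early has no stated post-survey time and might never be surveyed. The t-test would then compare intervention finishers with all usual-care dyads. Dyads in greater decisional conflict may be less likely to finish, so the groups could differ with no platform effect at all. A dyad that needs more than one sitting would also have a pre-to-post interval longer than the week used in the other arm.

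**Working it through.** **1. The two readings against the rest of the protocol**

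| Source | Completion = end of facilitated session | Completion = finished document |
|---|---|---|
| Study duration: two sessions | Fits: pre-survey and website, then post-survey | Fits only if every dyad finishes in one sitting |
| Design and Subject recruitment: intervention dyads complete pre and post surveys | Fits | Conflicts if non-finishers are skipped |
| Aim 2 text in Procedures | Same sequence, with completion as the session's activity | Aim 2 post-survey is not tied to a finished document |
| Usual-care timing | Matches: one week after that arm's own planning contact | Differs |

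The first reading fits every row. Under it, both arms are surveyed one week after the pre-survey session and selection bias is zero. The second reading causes bias only with two further steps: staff leave non-finishers unsurveyed, which no section tells them to do, and finishing is related to the score.

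**2. The plan's own figure**

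Inputs from the Analysis Plan: 25 per arm, 30% against 70% ACP completion, one-sided pooled Z-test at 0.05. Normal approximation:

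Φ[(0.40 − 1.645 × √(2 × 0.5 × 0.5/25)) / √(2 × 0.21/25)] = Φ[(0.400 − 0.233)/0.130] = 90.2%.

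Exact binomial enumeration of the same test gives 91.52%, which matches the stated 91.5%. No survey time enters this calculation.

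**3. Size on the adverse reading**

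Assume the true effect is zero, finishing depends on a normal latent variable with correlation ρ to the post score, a share P finishes, and only finishers are surveyed. Then

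bias in SD = ρ × φ(z_P)/P, where Φ(z_P) = P.

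For P = 0.70, φ = 0.348 and φ/P = 0.497; multiplying by ρ = 0.3, 0.5 and 0.7 gives 0.149, 0.248 and 0.348. The type I error is simulated for a two-sided 5% t-test with 25 per arm.

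| P | Dyads not surveyed, of 25 | Bias in SD (ρ = 0.3/0.5/0.7) | Type I error |
|---|---|---|---|
| 0.70 | 7.5 | 0.15/0.25/0.35 | 7%/12%/20% |
| 0.80 | 5 | 0.11/0.18/0.25 | 6%/9%/13% |
| 0.90 | 2.5 | 0.06/0.10/0.14 | 5%/6%/7% |
| 0.95 | 1.25 | 0.03/0.05/0.08 | 5%/5%/6% |

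Both P and ρ are assumptions. The 70% in the Analysis Plan is ACP completion, which the protocol does not equate with finishing the website, so that row is a low case. If change scores are tested and selection acts only through a stable trait, the type I error stays at about 5%.

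**4. Arm size**

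Current Status of Study shows enrolment closed, with 15 subjects at Penn and 7 at participating centers. It does not say whether the counts overlap, include Aim 2, or count dyads or individuals. The ceiling is 15 + 7 = 22 dyads, or 22/2 = 11 per arm. If the 22 are individuals, that is 11 dyads, or 5 to 6 per arm. At P = 0.70 the type I error is 6%/7%/10% with 10 per arm and 5%/6%/7% with 5 per arm. The 12% and 20% in the table therefore do not describe this trial. The bias in SD units does not depend on arm size.

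**The case for a change.** The case for a change is not empty. The wording does differ between arms, and only the Aim 3 intervention arm, where a randomised comparison depends on it, is tied to completion; the Aim 2 text shows that a plain one-week interval was available. Either Genesis staff or study personnel may give the surveys, at up to four facilities, so an undefined term could be applied differently from place to place. In a pilot the estimate matters more than the p-value, and the SD bias does not shrink in small arms. One sentence would settle the matter at almost no cost.

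What stands is that the term is undefined, that no fallback is written, and that the bias formula is right given its assumptions. What does not follow is that the plan excludes non-finishers. Silence on their timing is not an instruction to skip them, and two sections say that the intervention dyads complete both surveys. The link to the t-test is also an inference: the Design and Subject recruitment sections call the instruments confidence in decision making surveys, and only the Analysis Plan names the Decisional Conflict scale. With enrolment closed, a new timing rule would reach few dyads, if any. A clock started strictly at the pre-survey would have its own cost, since some dyads could answer before finishing the website.

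**Conclusion.** No change to the plan is needed. The protocol leaves one term undefined, and its other sections point to the sensible meaning: the post-survey falls one week after the facilitated session, for every intervention dyad. On that reading the arms share a schedule and there is no selection bias. Any harm needs a narrower reading, staff skipping non-finishers, finishing being correlated with the score, and the Decisional Conflict scale being part of the post-survey. The protocol states none of these. If all held, the bias would run from 0.03 SD (95% finishing, correlation 0.3) to 0.35 SD (70%, correlation 0.7), in a comparison labelled exploratory. The ACP-completion hypothesis and its 91.5% power do not depend on survey timing. Ordinary reporting of the numbers randomised and surveyed in each arm would show whether non-finishers were surveyed.

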### **The following documents are currently attached to this item:**

*There are no documents attached for this item.*

### **Deception**

Does your project use deception?

No

### **International Research**

Are you conducting research outside of the United States?

No

### **Analysis Plan**

We will use Z-tests to test our hypothesis that a significantly higher percentage of participants in the intervention group will complete an ACP compared with those in the usual care group. We adjust for participant characteristics due to the small sample size, but only the most important characteristics using likelihood ratio testing to avoid an overfit model. To generate new hypotheses, we will examine differences between groups with regard to demographic and clinical variables using parametric t-tests or nonparametric Wilcoxon tests (for continuous variables) and Fishers Exact tests for binary variables. To explore differences in Decisional Conflict scale scores, we will conduct a two-group independent T-test. Based on estimates derived from the Genesis EHR, we expect that 30% of PWD/SDM in the usual care arm will have a completed ACP within several weeks following admission to participating NHs. In the intervention arm, we estimate that 70% of SDMs/PWD will complete an ACP, as has been found among other OCW users (see Preliminary Studies). Enrolling 25 participants in each arm would yield 91.5% power to detect this difference of 70% vs. 30% ACP completion rate between the intervention and control groups. This calculation is based on a 1-sided Z-test with pooled variance and a significance level of 0.05.

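### The Analysis Plan gives two answers to its only powered hypothesis, a Z-test and a comparison adjusted for covariates selected on the trial's own outcomes, and does not say which decides

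*Combined protocol and SAP*

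**What the plan says.** All of the relevant text is in the Analysis Plan section.

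- The hypothesis and its test: "We will use Z-tests to test our hypothesis that a significantly higher percentage of participants in the intervention group will complete an ACP". The comparator is usual care.
- The next sentence opens with the adjustment: "We adjust for participant characteristics due to the small sample size". It then limits which covariates are kept: "but only the most important characteristics using likelihood ratio testing to avoid an overfit model".
- The power statement: 25 per arm gives 91.5% power for 70% against 30% completion. "This calculation is based on a 1-sided Z-test with pooled variance", at the one-sided level given as "a significance level of 0.05".

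The exploratory comparisons, meant to generate new hypotheses, start only in the sentence after the adjustment. Read in order, the adjustment belongs to the hypothesis test. No section names the covariates, the candidate pool, the selection threshold, the model or the effect measure, and none ranks the Z-test against the adjusted result.

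**The concern.** The pooled two-proportion Z-test behind the power statement contains no covariates. The adjusted comparison is therefore a second analysis of the same hypothesis, and its model is chosen by looking at the outcomes it will then be used to test. Testing the arm effect afterwards as if the model had been fixed ignores the search. In a small sample this can raise the false-positive rate and push the estimate away from no effect.

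With no rule on which result decides, the choice can also be made after both are known. This is the trial's only powered hypothesis, so the ambiguity falls on its main conclusion. The small sample is offered as the reason to adjust, but it is better read as a reason to fix very few covariates in advance.

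**Working it through.** **Inputs from the Analysis Plan.** Completion is 30% under usual care ("we expect that 30% of PWD/SDM in the usual care arm will have a completed ACP") and 70% under intervention ("In the intervention arm, we estimate that 70% of SDMs/PWD will complete an ACP"). There are 25 per arm, with a 1-sided pooled Z-test at 0.05.

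**Step 1: reproduce the stated power.**

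Normal approximation, pooled proportion 0.5:
- Standard error under the null: √(2 × 0.5 × 0.5 / 25) = 0.1414
- Standard error under the alternative: √((0.3 × 0.7 + 0.7 × 0.3) / 25) = 0.1296
- Power = Φ[(0.40 − 1.645 × 0.1414) / 0.1296] = Φ(1.29) = 90.2%

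Exact power sums Bin(x₁; 25, 0.7) × Bin(x₀; 25, 0.3) over all pairs of counts where the pooled Z exceeds 1.645. The result is 91.52%, which matches the plan. The same sum with 30% in both arms gives a true level of 4.99% (5.9% at 50% in both arms). The stated power therefore belongs to the unadjusted test.

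**Step 2: how often would selection pick up noise?** If candidates were independent, unrelated to outcome and each tested at 5%, the chance that at least one enters is 1 − 0.95⁵ = 23% with 5 candidates and 1 − 0.95¹⁰ = 40% with 10. In simulation the average number selected was 0.32 and 0.64. With 30% completion in both arms there are only 50 × 0.30 = 15 completions to fit.

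**Step 3: error rate after selection.** The plan gives no rule, so the following are assumptions:
- logistic regression with arm always in the model
- forward selection by likelihood ratio test at p<0.05
- 5 or 10 independent normal candidates, either all noise or with three prognostic (log-odds 0.5 per standard deviation)
- a 1-sided 5% signed-root likelihood ratio test of arm

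Rejection rates at 25 per arm with 30% in both arms (8,000 runs per row, Monte Carlo standard error about 0.3 points):

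| Candidates | Z-test | Two fixed covariates | Selected covariates | Either Z-test or selected model |
|---|---|---|---|---|
| 10, all noise | 4.8% | 5.8% | 6.5% | 6.7% |
| 10, three prognostic | 5.0% | 5.7% | 7.7% | 8.6% |
| 5, three prognostic | 4.8% | 5.6% | 6.4% | 7.1% |

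Variations, all at 25 per arm and 30% in both arms:
- Five noise candidates: about 5.1-5.8% across runs, no clear excess over two fixed covariates.
- Ten noise candidates, looser p<0.10 threshold, at most three selected (6,000 runs): 8.2% by likelihood ratio test and 7.4% by Wald test. The Z-test happened to run high in that set, at 5.6%.
- Covariates selected with arm left out of the model (2,500-3,000 runs): about 4.9-5.9%.

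**Step 4: estimate and power at 70% against 30%.** The true odds ratio is (0.7/0.3) / (0.3/0.7) = 5.44. With 10 noise candidates, selection at p<0.05 and arm in the model, the median selected-model odds ratio was 6.6 in one run and 6.7 in another, against 5.6 unadjusted. Power after selection was about 91%, against about 92% for the Z-test.

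**The case against.** The strongest reply is that the plan assigns the hypothesis to Z-tests and powers it on one, so the adjusted result may be only supportive. If the pooled Z-test alone decides, its level at the planned 30% rate holds (4.99%). That stands, and it is why the defect is that the plan leaves the choice open, not that the plan is bound to exceed 5%. It can also be said that a model coefficient can be tested with a Wald Z-test, so the word Z-test does not by itself rule out adjustment. That is true, but it leaves unclear which Z-test is meant.

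A second reply is that keeping few covariates overfits less than adjusting for all of them. This also stands, but a short list fixed in advance achieves the same without the search.

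A third is that the inflation is small and depends on assumptions. Two fixed covariates already give 5.6-5.8%, so part of the excess is small-sample logistic behaviour. A noticeable excess needs about 10 candidates, prognostic covariates or a loose threshold. This stands and limits the severity.

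A reader might infer several stronger points that the documents do not support:
- *The power figure is wrong.* It reproduces, and power after adjustment is about the same.
- *The inflation is much larger because the sample is really about 11 per arm.* The modification form's counts of 15 and 7 sum to 22, but they are not identified as randomised Aim 3 dyads, and the protocol also enrols Aim 2 participants.
- *A post-randomisation variable will be adjusted for.* The Procedures section does have staff "administer the post survey and COVID-19 survey one week after website completion", but nothing makes that survey a candidate covariate. The plan also refers to clinical variables, so the surveys are not the only possible source.
- *An inflated odds ratio will be reported.* The plan names no effect measure.

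**Conclusion.** The concern holds in a limited form. The only powered hypothesis has two analyses, one of them built by data-driven covariate selection, and no rule says which decides. The power statement is right for the unadjusted test.

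If the adjusted result decides, the 1-sided 5% error is about 5-8% at 25 per arm, and it reaches about 9% if the more favourable result may be quoted. If an odds ratio were reported, its median would drift from 5.4 to about 6.6-6.7 with 10 noise candidates, and nothing is gained in power.

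These sizes rest on an assumed 5 to 10 candidates, forward selection, thresholds of p<0.05 or p<0.10, and arm kept in the model. To say flatly that the 5% level fails, or that the error is uncontrolled, would go beyond the text and the numbers. For a randomised pilot of up to 50 dyads this is a should-fix.

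**What to change.** In the Analysis Plan:

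1. Name the unadjusted comparison of completion proportions (the 1-sided pooled Z-test already used for power) as the single primary analysis, with the difference in proportions as the effect measure.
2. Remove likelihood ratio covariate selection from the arm comparison.
3. If an adjusted result is wanted, make it a sensitivity analysis with one or two covariates fixed now and measured before allocation, for example site, or short- against long-term care. Report it as a risk difference, on the same scale as the hypothesis. Site uses one model term fewer than the number of facilities, so the list should stay very short.
4. Label any model with selected covariates exploratory, and bar variables measured after allocation from it.

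The cost is a few sentences of wording. It needs no new data and loses no power. The small downside is giving up the freedom to adjust for a chance imbalance noticed in the data.
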